6.7.2. Laboratory Data

Laboratory data will be listed and summarized in accordance with the Pfizer reporting standards. Summaries of incidence of clinically significant abnormalities will include frequency and percentages. Laboratory data criteria for discontinuation and abnormalities can be found in [Section 9.3](#).

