### **8.2.2. Abnormal Test Findings**

Abnormal objective test findings should be recorded as AEs when any of the following conditions are met:

- Test result is associated with accompanying symptoms; and/or
- Test result requires additional diagnostic testing or medical/surgical intervention; and/or
- Test result leads to a change in study dosing (outside of any protocol-specified dose adjustments) or discontinuation from the study, significant additional concomitant drug treatment, or other therapy; and/or
- Test result is considered to be an AE by the investigator or sponsor.

Merely repeating an abnormal test, in the absence of any of the above conditions, does not constitute an AE. Any abnormal test result that is determined to be an error does not require recording as an AE.

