**The following laboratory abnormalities require re-testing until resolution or agreement with Pfizer:**

Laboratory Variable	Laboratory Value	Re-testing Timeframe a
Hematology		
Absolute Neutrophil Count	<1000/mm  (<1.0 × 10  /L)	Within 1 week
Hemoglobin	<10.0 g/dL (<6.21 mmol/L or <100 g/L) OR Decrease of ≥2.0 g/dL from baseline	Within 1 week
Platelet count	<100,000/mm  (<100.0 × 10  /L)	Within 1 week
Absolute Lymphocyte Count b	<600/mm  (<0.6 × 10  /L)	Within 1 week
Serum Chemistry		
Creatine kinase c	>3 × ULN	Within 1 week
Aspartate aminotransferase	See Section 8.4.2 for potential cases of drug-induced liver injury.	Within 48 hours
Alanine aminotransferase	See Section 8.4.2 for potential cases of drug-induced liver injury.	Within 48 hours
Total bilirubin	See Section 8.4.2 for potential cases of drug-induced liver injury.	Within 48 hours

- Based on awareness of the abnormal results.
- Subjects with absolute lymphocyte count <500/mm^3 (0.5 × 10^9/L) will be reflex-tested for FACS-TBNC until the absolute lymphocyte count resolves or stabilizes at a level acceptable to the investigator and sponsor.
- In addition to re-testing creatine kinase >3 × ULN, urine myoglobin will be performed as reflex testing for any subject with creatine kinase >10 × ULN.

In case of positive urine pregnancy test, the subject will have study drug interrupted and a serum sample collected on the same day (or as soon as possible) and submitted to the central laboratory for pregnancy testing.

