### Laboratory Abnormalities:

All the following laboratory abnormalities **require discontinuation** if they are confirmed by re-test. Refer to the associated re-testing timeframes for laboratory abnormalities in [Appendix 3.1](#):

- Absolute Neutrophil Count <750/mm^3 (<0.75 × 10^9/L).
- Hemoglobin <9.0 g/dL (<5.59 mmol/L or <90 g/L) or a decrease of >30% from baseline (either criterion or both).
- Platelet count <75,000/mm^3 (<75.0 × 10^9/L).
- Absolute Lymphocyte Count <500/mm^3 (<0.5 × 10^9/L).

NOTE: Subjects with absolute lymphocyte count <500/mm^3 (0.5 × 10^9/L) will be reflex tested for FACS-TBNK until the absolute lymphocyte count resolves or stabilizes at a level acceptable to the investigator and sponsor.

- Creatine kinase  $>10 \times$  ULN.

NOTE: In addition to re-testing creatine kinase  $>3 \times$  ULN, urine myoglobin will be performed as reflex testing for any subject with creatine kinase  $>10 \times$  ULN.

- Aspartate aminotransferase (AST) or alanine aminotransferase (ALT) that meet ANY of the following:
  - $>3$  times the upper limit of normal with at least one total bilirubin value  $>2$  times the upper limit of normal;
  - $>3$  times the upper limit of normal accompanied by signs or symptoms consistent with hepatic injury (eg, new onset elevated PT/INR);
  - Two sequential AST or ALT elevations  $>5$  times the upper limit of normal, regardless of total bilirubin or accompanying signs or symptoms.

NOTE: In each case, there is a need for additional investigations, such as review of ethanol, recreational drug and dietary supplement consumption; testing for acute hepatitis A, B or C infection and biliary tract imaging should be promptly discussed with the sponsor or designee.

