9.3. Laboratory Data Criteria for Discontinuation and Abnormalities

Labs Meeting Discontinuation Criteria, as per Appendix 3.2 of the protocol

Table 7. Laboratory Values Meeting Discontinuation Criteria

		Criterion #1	Criterion #2
Hematology	Hemoglobin	<90 g/L or a decrease of >30% from baseline	n/a
	Platelets	<75 × 10 ⁹ /L	n/a
	Lymphocytes (ABSOLUTE)	<0.5 × 10 ⁹ /L	n/a
	Neutrophils (ABSOLUTE)	<0.75 × 10 ⁹ /L	n/a
Chemistry	Aspartate Aminotransferase	>3× ULN W/Bilirubin >2× ULN	Two Sequential Elevations >5× ULN
	Alanine Aminotransferase	>3× ULN W/Bilirubin >2× ULN	Two Sequential Elevations >5× ULN
	Creatine Kinase	>10× ULN	

Lab Test Abnormalities

Table 8. Laboratory Test Abnormalities

		Lower Limit	Upper Limit
Hematology	Hemoglobin	<0.8× LLN	n/a
	Hematocrit	<0.8× LLN	n/a
	Red Blood Cell Count	<0.8× LLN	n/a
	MCV	<0.9× LLN	>1.1× ULN
	MCH	<0.9× LLN	>1.1× ULN
	MCHC	<0.9× LLN	>1.1× ULN
	Platelets	<0.5× LLN	>1.75× ULN
	White Blood Cell Count	<0.6× LLN	>1.5× ULN
	Reticulocytes	<0.5× LLN	>1.5× ULN
	Reticulocytes/Erythrocytes	<0.5× LLN	>1.5× ULN
	Leukocytes	<0.6× LLN	>1.5× ULN
	Lymphocytes (ABSOLUTE)	<0.8× LLN	>1.2× ULN
	Lymphocytes/Leukocytes	<0.8× LLN	>1.2× ULN
	Neutrophils (ABSOLUTE)	<0.8× LLN	>1.2× ULN
	Neutrophils/Leukocytes	<0.8× LLN	>1.2× ULN
	Basophils/Leukocytes	n/a	>1.2× ULN
	Eosinophils	n/a	>1.2× ULN
	Eosinophils/Leukocytes	n/a	>1.2× ULN
	Monocytes	n/a	>1.2× ULN
	Monocytes/Leukocytes	n/a	>1.2× ULN
Prothrombin Time	n/a	>1.1× ULN	
Basophils	n/a	>1.2× ULN	

Table 8. Laboratory Test Abnormalities

		Lower Limit	Upper Limit
	Prothrombin Intl. Normalized Ratio	n/a	>1.1× ULN
Chemistry	Blood Urea Nitrogen	n/a	>1.3× ULN
	Urea	n/a	>1.3× ULN
	Creatinine	n/a	>1.3× ULN
	Glucose	<0.6× LLN	>1.5× ULN
	Calcium	<0.9× LLN	>1.1× ULN
	Sodium	<0.95× LLN	>1.05× ULN
	Potassium	<0.9× LLN	>1.1× ULN
	Chloride	<0.9× LLN	>1.1× ULN
	Bicarbonate	<0.9× LLN	>1.1× ULN
	Aspartate Aminotransferase	n/a	>3.0× ULN
	Alanine Aminotransferase	n/a	>3.0× ULN
	Bilirubin	n/a	>1.5× ULN
	Direct Bilirubin	n/a	>1.5× ULN
	Indirect Bilirubin	n/a	>1.5× ULN
	Alkaline Phosphatase	n/a	>3.0× ULN
	Uric Acid	n/a	>1.2× ULN
	Albumin	<0.8× LLN	>1.2× ULN
	Creatine Kinase	n/a	>2.0× ULN
	Cholesterol	n/a	>1.3× ULN
	HDL Cholesterol	<0.8× LLN	n/a
LDL Cholesterol	n/a	>1.2× ULN	
Triglycerides	n/a	>1.3× ULN	
Protein	<0.8× LLN	>1.2× ULN	
Gamma Glutamyl Transferase	n/a	>3.0× ULN	
Urinalysis	pH (Scalar)	<4.5	>8
	Glucose (Scalar)	n/a	≥1
	Ketones (Scalar)	n/a	≥1
	Protein (Scalar)	n/a	≥1
	Hemoglobin (No Unit)	n/a	≥1

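### SAP Section 9.3 has no platelet category at the protocol's own re-test level of 100 × 10⁹/L, which leaves a gap in the categorical laboratory summary by arm

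*SAP*

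**What the plan says.** Protocol Section 2 and SAP 3.4 list the incidence of clinically significant abnormalities in laboratory values as a safety endpoint. SAP 6.7.2 provides the analysis: "Summaries of incidence of clinically significant abnormalities will include frequency and percentages". It refers to Section 9.3 for the criteria, and that section holds two tables:

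- Table 7 repeats the protocol's discontinuation limits. For platelets this is below 75 × 10⁹/L.
- Table 8 gives the abnormality limits. Its platelet row reads "Platelets <0.5× LLN >1.75× ULN".

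Protocol Appendix 3.1 works at a higher platelet level. Under the lead-in "The following laboratory abnormalities require re-testing until resolution or agreement with Pfizer" it lists platelets below 100 × 10⁹/L, with a repeat within one week. For hemoglobin it lists a value below 10.0 g/dL or a "Decrease of ≥2.0 g/dL from baseline". Appendix 3.2 requires discontinuation for platelets below 75 × 10⁹/L, but only "if they are confirmed by re-test".

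**The concern.** Platelets are a parameter with an observed drug effect. Protocol 1.4.1 reports a mean fall of 18% during four weeks of 200 mg in the alopecia study, and Protocol 1.4.2 a median fall of 25% in the arthritis study. This trial compares regimens with and without a 200 mg loading phase. A natural safety question is therefore how many subjects in each arm drop below the level at which the protocol itself calls for action.

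The SAP specifies no count at that level. Whether Table 8 adds anything above the stopping limit depends on a reference limit that neither document states. Adverse event tables are not a dependable substitute, because Protocol 8.2.2 says that "Merely repeating an abnormal test, in the absence of any of the above conditions, does not" constitute an AE. At stake is one line of the categorical laboratory summary, not an efficacy result or a subject-protection rule.

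**Working it through.** **Inputs**

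| Quantity | Value | Source |
|---|---|---|
| Re-test level, platelets | <100 × 10⁹/L | Protocol Appendix 3.1 |
| Stopping limit, platelets | <75 × 10⁹/L, confirmed | Protocol Appendix 3.2 (75 repeated in SAP Table 7) |
| Reporting limit, platelets | <0.5 × LLN | SAP Table 8 |
| Entry floor, platelets | excluded if <150 × 10⁹/L | Protocol 4.2, criterion 24c |
| Earlier falls at 200 mg | 18% mean, 25% median | Protocol 1.4.1, 1.4.2 |
| Platelet LLN | not given | assumed 125 to 200 |

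Units agree: 75,000/mm³ = 75 × 10⁹/L and 100,000/mm³ = 100 × 10⁹/L. The stopping limit of 75 cannot be reproduced from 0.5 × LLN without an LLN, so the comparison is run over a range.

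**Step 1. Table 8 limit = 0.5 × LLN**

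| Assumed LLN | Table 8 limit | Against 75 | Counted in neither table |
|---|---|---|---|
| 125 | 62.5 | below | 75 to <100 |
| 140 | 70.0 | below | 75 to <100 |
| 150 | 75.0 | equal | 75 to <100 |
| 155 | 77.5 | above | 77.5 to <100 |
| 165 | 82.5 | above | 82.5 to <100 |
| 200 | 100.0 | above | none |

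Break-even points: 0.5 × LLN = 75 gives LLN = 150, and 0.5 × LLN = 100 gives LLN = 200. So Table 8 is looser than the re-test level for every LLN below 200, and adds nothing above the stopping limit for every LLN of 150 or less.

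**Step 2. Where the known average fall lands.** For a subject at the entry floor, 150 × (1 − 0.18) = 123.0 and 150 × (1 − 0.25) = 112.5, both above every limit. From 150, reaching 100 takes a fall of 1 − 100/150 = 33.3%; reaching 75 takes 1 − 75/150 = 50%. A count below 100 therefore describes the tail, not the average shift.

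**Step 3. Illustration of size (assumed inputs, not from the documents).** Baseline normal with mean 230 to 270 and SD 50 to 60, truncated at 150; mean change −18% or −25%; SD of change 10 to 20 percentage points; one assessment per subject. By simulation:

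- below 100: 0.10% to 7.75%, which is 0.1 to 9.3 per group of 120;
- below 75: 0.001% to 2.295%, which is 0 to 2.8 per group of 120.

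A second set (baseline mean 240 to 260, SD 55 to 60, within-subject CV 15% to 20%, same falls) gives 0.18% to 1.44% below 100, or 0.4 to 3.5 of the 240 loaded subjects, and 0.001% to 0.046% below 75.

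**Step 4. Hemoglobin.** Take a subject who goes from 15.0 to 12.5 g/dL. The fall of 2.5 g/dL meets the Appendix 3.1 criterion. It is 2.5/15.0 = 16.7%, so it misses Table 7 (below 90 g/L or a fall over 30%). Table 8 counts below 0.8 × LLN and would include the subject only if LLN > 12.5/0.8 = 15.6 g/dL. Neither table has a row for the 2.0 g/dL fall.

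**Step 5. Comparison row.** Creatine kinase uses the ULN throughout: reported above 2 × (Table 8), re-tested above 3 × (Appendix 3.1), stopped above 10 × (Appendix 3.2). There the reporting category opens before the action levels. For platelets it opens after the re-test level unless the LLN is 200 or more.

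**The case against.** Four points weigh on the other side.

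- **Different purposes.** Appendix 3.1 triggers re-testing; it does not define a reportable abnormality. A reader might infer that protocol and SAP contradict each other. They do not: this is an omission in reporting, and Table 8 can stand as the sponsor's reporting standard.
- **The platelet effect stays visible.** A reader might infer that the planned output cannot show the drug's known platelet effect. That goes too far. SAP 6.7 plans N, mean, median, SD, graphs and selected listings, and an average fall of 18% to 25% would appear there. As Step 2 shows, a count below 100 would not display that average.
- **The AE route exists.** The sentence in Protocol 8.2.2 applies only when none of its listed conditions is met, and those include the investigator or sponsor judging the result to be an AE. Protocol 7.5.7 also asks for clinically significant abnormal findings to be recorded as AEs. Some values between 75 and 100 can reach the AE tables, but by judgement, so those tables do not give a uniform count by arm.
- **The stopping-limit comparison is conditional.** A reader might take Table 8's limit to lie at or below 75 as a fact. It does so only if the LLN is 150 or less, and the entry floor of 150 is not stated to be the LLN. Stopping also needs a confirmed value while neither SAP table states a confirmation rule, so a subject can be counted without having met the stopping rule.

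The counts may also be small, so a new row might read near zero in some arms. That is fair, but a small count at the protocol's action level is still informative for safety.

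**Conclusion.** The gap is real but narrow. For any platelet LLN below 200, no incidence count specified in the SAP matches the protocol's re-test level. If the LLN is 150 or less, the summary for this safety endpoint counts nobody between 75 and under 100 × 10⁹/L; at an LLN of 155 to 165, most of that interval is still missed. The first statement needs only arithmetic; the second rests on an LLN that the documents do not give.

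No single percentage of missed events should be quoted. A reader might infer that nearly all values below 100 would go uncounted. With the limit at 75, the first set of assumptions in Step 3 puts the uncounted share anywhere from about 70% (1 − 1.420/4.68) to over 99% (1 − 1/137, from a ratio of 137 between the two probabilities), depending on assumed variability.

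This is a minor reporting improvement. It has no bearing on efficacy conclusions or on how subjects are monitored.

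**What to change.** In SAP 9.3:

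1. State the platelet LLN to which Table 8 applies. Protocol Appendix 6.3 allows local laboratories with their own reference ranges during public emergencies, so say whether the LLN is common or laboratory-specific.
2. Add a row for platelets below 100 × 10⁹/L beside the standard 0.5 × LLN row, not in place of it.
3. Optionally, add a row for the Appendix 3.1 hemoglobin fall of at least 2.0 g/dL from baseline.
4. Tabulate the new rows by treatment group to Week 24, while the placebo comparison is intact.

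The cost is one or two study-specific rows beyond the sponsor's standard limits and one programmed summary, with possibly small counts. Keeping the standard row preserves comparison with the sponsor's other studies. No monitoring, re-test or stopping rule is altered.

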6.7.3. Vital Signs, including Height and Weight

Vital signs will be summarized at baseline and all post-baseline visits. The data will be listed and summarized in accordance with the Pfizer reporting standards. Summaries of incidence of clinically significant abnormalities will include frequency and percentages.

Height and weight will be summarized at enrollment/baseline, Week 24, and Week 48.

6.7.4. Electrocardiogram

Abnormal ECG findings will be summarized.

6.7.5. Physical Examination

Physical examinations will be summarized at baseline and all-available post-baseline visits.

6.7.6. Hearing Examination

Audiometry will be performed at screening, Week 24, and Week 48 visits. Summaries of incidence of clinically significant worsening in hearing from screening, as assessed by the investigator following review of the audiometry reports, will be presented.

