### 1.3. Nonclinical and Phase 1 Efficacy and Safety Data

Data from nonclinical and Phase 1 programs supports the planned clinical trials with PF-06651600.

The no observed adverse effect levels (NOAEL) in the 6-month rat and second 9-month dog studies were 200 and 10 mg/kg/day, respectively. In the second 9-month dog toxicity study, the NOAEL of 10 mg/kg/day was based on adverse over-immunosuppression and axonal dystrophy (not axonal degeneration) in the central nervous system and peripheral nervous system at  $\geq 20$  mg/kg/day, accompanied by functional auditory deficits (brainstem auditory evoked potentials) at the highest dose of 40 mg/kg/day (a 29-fold exposure multiple relative to the clinical dose of 50 mg). The area under the concentration-time curve (AUC) exposure margins in this study at the NOAEL at study end were approximately 1.5x and 6.5x relative to the predicted exposure at the 200 mg and 50 mg clinical doses, respectively.

Further information is available in the current version of the Investigator's Brochure (IB).

The potential for PF-06651600 to be involved in drug-drug interaction (DDI) is being investigated. If results exclude a clinically meaningful DDI (eg, relative to AUC) between PF-06651600 and a perpetrator or victim drug then that perpetrator or victim drug will no longer be prohibited as a concomitant medication; this information will be communicated via an administrative letter. Refer to [Section 5.8.2](#) for medications prohibited to be used prior to and during the study.

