#### **1.4.2. Phase 2a Study in Rheumatoid Arthritis**

The completed Phase 2a study B7981006 was an 8-week randomized, double-blind, placebo-controlled, parallel-group, multi-center study in subjects with moderate-to-severe active rheumatoid arthritis (RA) with an inadequate response to methotrexate. A total of 70 subjects were randomized to study treatment; 28 subjects received placebo and 42 subjects received PF-06651600 (200 mg QD).

PF-06651600 was determined to be generally safe and well tolerated in this study. There were no deaths or SAEs. TEAEs were numerically higher in subjects receiving PF-06651600 compared to those receiving placebo. The TEAEs reported in more than 5% subjects with RA receiving PF-06651600 were influenza and lymphopenia. The majority of the TEAEs were mild in severity. There was 1 mild case of herpes simplex in the PF-06651600 group that was considered to be treatment-related with no cases in the placebo group. There were no clinically relevant changes in vital signs, electrocardiogram (ECG), or audiometric assessments. By the Week 8 time point (as early as 2 weeks), in the PF-06651600 group, there were decreases in the median platelet counts (25% change from baseline), lymphocyte counts (21% change from baseline), neutrophil counts (24% change from baseline), and hemoglobin (3% change from baseline). None of these were deemed to be clinically relevant by the investigator and values returned to near baseline by the 12-week follow-up visit.

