### **7.5.5. Audiological Evaluation**

All subjects will have an audiological evaluation at times specified in the [Schedule of Activities](#). When possible, the subject should have the audiological evaluation performed at the same evaluation center during the study.

A full audiological evaluation must be completed at Screening or within 8 weeks prior to Day 1. This evaluation includes audiological history, otoscopic examination, pure tone audiometry, air and bone conduction, speech audiometry, and immittance audiometry. All audiological results must be available prior to Day 1 to assess eligibility.

At subsequent visits, updated audiological history, otoscopic examination, and pure tone audiometry will be performed; based upon results, additional audiometry assessments may be required.

For subjects who terminate early from the study, efforts must be made to complete the audiological evaluation.

If there is a clinically meaningful, treatment-emergent decline in hearing from baseline, the subject must be promptly evaluated by a medically qualified specialist to assess for possible causes. Evaluation results should then be discussed with the Sponsor to determine if the subject should be discontinued from the study. Discontinued subjects must be followed up off-treatment with appropriate testing at regular intervals, until hearing returns to baseline or is determined to be clinically stable.

Refer to the most current version of the Audiometry Study Guide for details on auditory evaluation. All procedures must be performed as per the Audiometry Study Guide.

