### Adverse Events:

- Serious infections, defined as any infection (viral, bacterial, and fungal) requiring parenteral antimicrobial therapy or hospitalization for treatment or meeting other criteria that require the infection to be classified as serious adverse event;
- Treatment-related SAEs;
- Clinically meaningful, treatment-emergent declines in hearing from baseline (refer to Audiometry Study Guide for details) are to be discussed with the Sponsor for possible withdrawal from the study;
- Other serious or severe AEs, at the discretion of the investigator or sponsor.

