## Audiological Evaluation

At visits after Screening which require audiological evaluation, if the subject is unable to visit the study site or designated ancillary center for audiological evaluation, the audiological history (Part 1 in the Audiometry Study Guide Worksheet for Post Day 1 visits) must be collected during the remote visit per [Appendix 6.2](#) (or during the home health visit per [Appendix 6.5](#)). The audiological evaluation must be performed per [Section 7.5.5](#) at the next available opportunity, even if outside of a protocol-specified visit window.

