6.7. Safety Summaries and Analyses

Safety analysis will be based on the safety analysis set (SAS).

Safety data will be presented in tabular and/or graphical format and summarized descriptively, where appropriate. All safety endpoints will be listed and summarized in accordance with Pfizer Standards. Categorical outcomes (eg, AEs) will be summarized by subject counts and percentage. Continuous outcome will be summarized using N, mean, median, standard deviation, etc. Selected subject listings will be produced for these safety endpoints accordingly.

In order to report the impact of COVID-19 on clinical trial populations and study data, the following additional listings and summaries will be produced:

- Listing of subjects affected by COVID-19 related study disruption;
- Protocol deviations related to COVID-19;
- Summary of drug interruption before and after the COVID-19 pandemic anchor date (09 January 2020 for Taiwan/China sites, and 11 March 2020 for the remaining countries);

- Discontinuations from study drug due to COVID-19 related AEs.

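### SAP 6.7.6 plans only an investigator-judged incidence of hearing worsening; the scheduled pure-tone thresholds have no pre-specified comparison by regimen

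*SAP*

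**What the plan says.** - SAP 6.7.6 (Hearing Examination) places audiometry at Screening, Week 24 and Week 48 and commits to one result: "Summaries of incidence of clinically significant worsening in hearing from screening, as assessed by the investigator following review of the audiometry reports, will be presented". It gives no frequencies, decibel cut-off or change-from-screening summary, and does not say that the incidence will be shown by regimen.
- SAP 6.7 has a general rule: "Continuous outcome will be summarized using N, mean, median, standard deviation, etc". It does not mention audiometry.
- Hearing is not among the safety endpoints in SAP 3.4, nor on the list in Protocol 9.5.
- Protocol 7.5.5 requires pure-tone audiometry at Screening (or within 8 weeks before Day 1). At later audiology visits "updated audiological history, otoscopic examination, and pure tone audiometry will be performed". The Schedule of Activities adds Early Termination.
- Protocol 1.3 reports, in the second 9-month dog study, "functional auditory deficits (brainstem auditory evoked potentials) at the highest dose of 40 mg/kg/day", described as a "29-fold exposure multiple relative to the clinical dose of 50 mg".
- Protocol 1.4.2, on the rheumatoid arthritis study (42 treated subjects, 8 weeks), states: "There were no clinically relevant changes in vital signs, electrocardiogram (ECG), or audiometric assessments".
- Protocol Appendix 3.2 lists for discussion of withdrawal: "Clinically meaningful, treatment-emergent declines in hearing from baseline (refer to Audiometry Study Guide for details"). That guide is not among the documents.
- Protocol Appendix 6.3 has audiograms missed because of a public emergency done "at the next available opportunity, even if outside of a protocol-specified visit window".

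**The concern.** The protocol treats hearing as a special concern, and schedules a quantitative test for about 660 subjects. The plan then commits only to a yes/no judgement by each investigator. A small shift common to many subjects in a regimen could leave few of them individually flagged. Week 24 is the last audiogram with a placebo control, because sequences F and G then start active drug. If the frequencies, the handling of two ears and the usable audiograms are chosen after unblinding, the comparison loses much of its value, whether it shows a signal or reassures.

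**Working it through.** **No plan figure to reproduce.** The documents give no margin, power or sample size for hearing.

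**Group sizes.** 660 subjects allocated 2:2:2:2:1:1:1 give 120 in each of four regimens, 60 on 10 mg, and 60 + 60 = 120 on pooled placebo to Week 24.

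**Assumptions, not document values.** Change in threshold is Normal with SD 5, 6 or 8 dB; two-sided alpha 0.05. A flag is a change at or above a cut-off, so the flag rate is P(Z ≥ (cut-off − shift)/SD). Investigator judgement is not a fixed cut-off, so a flag only approximates the planned table. Power for the mean is from the two-sample t test (noncentral t). Flag power is by full enumeration.

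**Case 1: everyone on active shifts by 3 dB**

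| | SD 5 | SD 6 | SD 8 |
|---|---|---|---|
| 10 dB flag rate, placebo v active | 2.3 v 8.1% | 4.8 v 12.2% | 10.6 v 19.1% |
| 120 v 120: mean | 0.996 | 0.971 | 0.825 |
| 120 v 120: flag, Fisher | 0.408 | 0.446 | 0.388 |
| 120 v 120: flag, uncorrected chi-square | 0.541 | 0.563 | 0.465 |
| 60 v 120 (10 mg): mean | 0.965 | 0.882 | 0.655 |
| 60 v 120 (10 mg): flag, Fisher | 0.404 | 0.382 | 0.306 |

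The mean has limits: a 2 dB shift at SD 8 has power 0.488 (120 v 120) or 0.349 (60 v 120). A 5 dB shift would usually show with the 10 dB flag (0.961/0.949/0.870, 120 v 120, Fisher).

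**Case 2: 10% on active lose 20 dB, the rest do not change (120 v 120)**

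| | SD 5 | SD 6 | SD 8 |
|---|---|---|---|
| Mean (Welch t, simulated, approximate) | 0.66 | 0.56 | 0.39 |
| 10 dB flag, Fisher | 0.79 | 0.60 | 0.34 |
| 15 dB flag, Fisher | 0.93 | 0.83 | 0.50 |

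The 15 dB flag beats the mean at every SD; the 10 dB flag does so at SD 5 and 6.

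**Precision of a descriptive interval.** Half-width = 1.96 × SD × √(1/n1 + 1/n2), at SD 5/6/8:
- 120 v 120: 1.27/1.52/2.02 dB
- 60 v 120: 1.55/1.86/2.48 dB
- 20% missing, 96 v 96: 1.41/1.70/2.26 dB
- 20% missing, 48 v 96: 1.73/2.08/2.77 dB

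**Visit windows if thresholds were tabulated by visit (SAP 9.1, Table 6).** Audiometry is not scheduled at every visit, and SAP 9.1 moves an off-schedule result to the next scheduled one.
- Early-termination audiogram on Day 40: falls in the Week 4 window (Days 22 to 42) and moves to Week 24.
- Delayed Week 24 audiogram after the first extension dose, on or before Day 179: Week 24 requires a date no later than the first extension dose, and Week 26 starts at Day 180. With the extension starting on Day 169 and the audiogram on Day 175, it falls in no window.
- Delayed audiogram after the first extension dose, Day 180 or later: moves toward Week 48, unless another audiogram is closer to Day 337.

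**The case against.** The best objection is that nothing is missing: SAP 6.7 already gives N, mean, median and SD for continuous outcomes, and sponsor standards and the Audiometry Study Guide may supply the rest. It stands in part: a threshold table is not ruled out, so a reader who infers that the SAP excludes thresholds goes too far. But the general sentence fixes no frequencies, ear rule, contrast or usable audiograms.

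A second objection is that the sensitivity argument depends on the shape of the effect. This stands. A reader might infer that a mean is simply the better measure; Case 2 shows otherwise, and averaging ears would turn a one-sided 20 dB loss into 20/2 = 10 dB. The size of the contrast in Case 1 also depends on the test, and neither test is planned, since safety is descriptive.

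Third, the visit-window problem belongs to the proposed table, because SAP 6.7.6 promises no by-visit display. This is right, and the windows matter here only as part of specifying that table.

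Fourth, individual safeguards exist: specialist evaluation of a meaningful decline, discussion with the sponsor, adverse event reporting and an external monitoring committee. They protect individuals but do not supply a between-regimen threshold contrast.

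Finally, the dog deficit was in evoked potentials, and the documents link it to no pure-tone value. That is also correct.

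**Conclusion.** The point holds as a low-cost improvement, not an error in a stated figure or a conflict between documents. The SAP commits to an investigator-judged incidence and leaves the scheduled thresholds without a pre-specified comparison by regimen. Under the assumed uniform 3 dB shift, a mean-change summary at 120 v 120 has 82 to 99.6% power, against 39 to 45% (Fisher) or about 46 to 56% (chi-square) for a 10 dB flag. With large losses in a minority the order reverses against a 15 dB flag, so both displays are needed. The shift, SD, Normal form and cut-offs are all assumptions.

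A reader might infer that the drug harms hearing in people. The documents do not support that: the dog finding was at 29-fold the 50 mg exposure, the earlier audiometric data in 42 treated subjects were reassuring though limited, and no clinically relevant mean shift is given. Nor do the documents show that thresholds are in the database; SAP 6.7.6 refers only to audiometry reports.

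**What to change.** Before unblinding, add to SAP 6.7.6, on the safety analysis set and labelled descriptive:

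1. Change from Screening in one pure-tone average and one high-frequency average, with frequencies named in advance. Show the two-ear average and, beside it, the worse ear.
2. At Week 24, each of the five regimens v pooled placebo, with a 95% CI for the two-ear averages. At Week 48, summaries by treatment sequence.
3. For this table, only audiograms in the actual Week 24 window (on or before the first extension dose) or the actual Week 48 window. List early-termination and late audiograms separately instead of applying the SAP 9.1 roll-forward.
4. Keep the investigator-assessed incidence, show it by regimen, and cite the Audiometry Study Guide criterion if there is one.

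Cost: a few tables and some wording; no new test or reader. Two averages × five regimens = 10 Week 24 intervals, of which 10 × 0.05 = 0.5 would be expected to exclude zero by chance. Intervals for the worse ear too would double this to 20 intervals and about 1. The sponsor should first confirm whether thresholds are in the database; if not, up to about 660 × 3 = 1,980 scheduled audiograms would have to be transferred or keyed.
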